## Tracking and Retention

In order to achieve the aims of the study, significant effort will be made to insure high levels of retention throughout the study. Procedures that could be used to support high retention rates will include: (1) collecting names, addresses, and phone numbers of relatives and friends who are likely to know the contact information of the participants; (2) contacting participants with personalized letters and cards; (3) setting up a password protected electronic database with names, addresses, phone numbers, and projected times of proposed contacts for all participants; and (4) maintaining phone contact with participants throughout the study and reminding participants in advance of study appointments. If a participant misses a visit or a telephone call, this must be rescheduled within a week. If 3 consecutive visits are missed, the participant will be dropped from the study.

## Management of Serious Adverse Events (SAE)

As mentioned in the prior sections, study participants will be screened for adverse events and serious adverse events by the study team. Regarding SAEs, we will utilize standard FDA classification and forms for SAEs handling and reporting. In general, SAEs will be defined as any event that:

- results in death
- is life threatening
- requires hospitalization (or a prolongation of hospitalization in already hospitalized participants)
- results in a persistent or significant disability or incapacity
- are congenital anomalies or birth defects
- any other adverse event that, based upon appropriate medical judgment, may jeopardize the subject's health and may require medical or surgical intervention.

For the purpose of this study, treatment-emergent mania (as defined previously), treatment-emergent skin rash and treatment-emergent-worsening suicidality (as defined previously) will be treated as SAEs and then will follow the same procedures as any SAE with regards to reporting timelines.

Mayo Clinic's IRB defines an unanticipated problem/event involving risk to subjects or others (UPIRTSO) as any problem or event that was 1) serious; 2) unanticipated; AND 3) at least possibly related to the research procedures. The Investigator shall assess whether a problem/event may be an Unanticipated Problems Involving Risk to Subjects or Others (UPIRTSOs). The Investigator will report UPIRTSOs as follows: If the UPIRTSO Occurs at Mayo Clinic or a site for which the Mayo Clinic IRB serves as the IRB of Record the principle investigator will submit to the IRB by completing the UPIRTSO form as soon as possible, but no later than 5 working days after the Investigator first learns of the problem/event. If the UPIRTSO occurs at a Non-Mayo site, the study team will submit to the IRB at time of continuing review as well as submit a modification to the protocol if other monitoring bodies (e.g. IRB at the site where the UPIRTSO occurred, or the Data Safety Monitoring Board) require changes to the protocol as a result of the non-Mayo Clinic problem/event. Non-UPIRTSOs will be reported at the time of continuing review. The PI will submit a brief narrative summary describing the nature, type, and frequency of events that have occurred since the last progress report. Additionally, the PI will continually monitor severity and frequency of non-UPIRTSO events throughout the course of the study and consider whether any changes caused such events to be considered UPIRTSOs. The external site PI will be in charge of reporting the SAE to the local IRB in less than 5 business days according to each IRB policy. The external PI will report the UPIRTSO/SAE to the Mayo PI.

Table 4. Summary of biospecimen collection in the FLAME Study.

	Baseline*	Week 2	Week 4	Week 16	Total volume in study
Laboratory tests	15 ml	-	-	-	-
Genomic/Biomarker	55 ml	55 ml	55 ml	-	-
Drug levels	-	10 ml	10 ml	10 ml	-
Total volume per visit	70 ml	65 ml	65 ml	10 ml	210 ml

### Biospecimen

1. Baseline: Venipuncture will be performed using standard techniques. A total of 70 mL blood sample will be collected at baseline, taking into account laboratory tests and genetic studies.

The samples are detailed as follows:

1. a. Laboratory tests: A total of 15 mL will be collected for laboratory tests. One 10-mL EDTA tube (CBC, 10 mL total sample) and into one 10 mL no-additive serum tube (electrolyte panel, TSH, AST/ALT and pregnancy test; 5 mL total sample).

2. b. Biomarkers: Within the same informed consent for the FLAME Study, participants will be additionally asked to participate in biomarker epigenetic and metabolomic/proteomic studies. These two additional blood samples will be drawn at week 2 and 4 of the comparative effectiveness trial. Approximately, two blood samples of 55 mL each, with the same characteristics of blood collected in the 3BD Disease Risk Program (IRB-08-008794) will be collected from each participant that accepts to participate in the biomarker studies (see table 5)

2. Subsequent visits: Biomarker and drug levels

2. a. Drug levels: At week 2, 4 and 16, a total of 10 mL will be collected for blood drug level of fluoxetine and its metabolite norfluoxetine (5 mL); and lamotrigine (5 mL), in one 10 mL no-additive serum tube.

2. A total of 210 mL blood sample will be collected throughout the study for these participants, taking into account laboratory tests, blood drug levels, genetic and biomarker studies as summarized in Table 4.

3. Urine Pregnancy and Toxicology testing may not need repeating if the subject is screened and enrolled as an inpatient and these labs were already performed.

Table 5. Biomarker and Genetic Breakdown

Sample Type	Number of Tubes	Total Volume	Aliquots
Blood No Additive (10mL) Red top	2	20 mL	8 mL serum: 4 in 1 ml 6 in .5 5 in .2 12 ml RBC destroyed

EDTA (10mL) Lavender top	2	20 mL	4 ml DNA 125 ug 8 ml plasma: 4 in 1 ml 6 in .5 5 in .2 Buffy coats (WBCs) x 3: proteins (signaling proteins and enzymes) and DNA 125 ug Total DNA: 250 ug
Sodium Heparin (10mL)	1	10 mL	Cryopreserved PBMCs x 3
PAXgene Blood RNA tube (2.5ml) Clear	2	5 mL	Extract 1 tube (6 ug RNA) to calculate RIN number (quality of RNA) Freeze 1 tube RIN number
Total	7 tubes	55 mL	

\* See 1.b. in this section. If the participant did not enroll in the 3BD Disease Risk Program (IRB-08-008794), or did so more than a month before enrolling the FLAME Study; a separated blood draw of 55 mL, with the same characteristics, will be collected as baseline sample (the total blood collection for this participant would be of 245 ml).

If the participant only consented to this study, his/her samples will be destroyed at the end of the study. Blood samples will be stored for the duration of the FLAME Study including all data and sample analysis.

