### **AIMS:**

1. To evaluate the association between genotype and haplotype variations in candidate genes involved in pharmacodynamic and pharmacokinetic pathways of treatment response to lamotrigine (n=200) or fluoxetine (n=200) in bipolar depression. In addition, we aim to perform exploratory analyses of single-nucleotide polymorphisms (SNPs) obtained from GWA studies with drug response phenotypes.
2. To evaluate the association between genotype and haplotype variations in candidate genes involved in pharmacodynamic and pharmacokinetic pathways of drug adverse events to treatment [rash emergence and antidepressant induced mania (AIM+) to lamotrigine (n=200) or fluoxetine (n=200) respectively in bipolar depression. In addition, we aim to perform exploratory analyses of single-nucleotide polymorphisms (SNPs) obtained from GWA studies with drug adverse events phenotypes.

3. To identify blood and brain metabolites associated with treatment response to lamotrigine (n=200) and fluoxetine (n=200) in bipolar depression.

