Selected participants may be asked to have their SCID interview audio/videotaped. These participants would be selected by the investigator and would sign a separate consent allowing permission to be taped. This tape would only be identified with the participant's study identifier and kept in a locked file. The purpose of these tapes would be to be used for inter rater reliability and quality assurance across the multi-site project.

If a participant fulfills all inclusion and exclusion criteria and he/she is not on an antidepressant at the screening visit, can continue directly to the enrollment visit and be randomized.

If the participant was on an antidepressant at the time of the screening visit, he/she is willing to discontinue it and it would be clinically reasonable to stop it, then the antidepressant will be tapered off in 1 week. The participant will have to be at least 7 days completely off the antidepressant before randomization. Then, the total number of days from screening to enrollment for these participants will be 14 days.

Patients enrolling in FLAME will also be given the option to participate in a separate study called 1H-MR Spectroscopy Before and After Treatment with Lamotrigine or Fluoxetine in Bipolar Depression (IRB 13-003660). This study is designed to only recruit subjects who participate in FLAME. This study will be conducted in tandem with FLAME.

Enrollment/baseline/randomization visit (could be at the same day of screening visit)

After consent is obtained and eligibility has been confirmed (inclusion/exclusion criteria; SCID, questionnaire ratings and blood drawn), RAVE® randomization case report form (CRF) will be submitted. Randomization will be done using blocking (blocks of 6 participants), and by study site with RAVE® (License) randomization tool. Block randomization will be utilized to assure balance between the 2 treatment arms. BPI disorder participants, who are randomized to fluoxetine and were not receiving any mood stabilizers at the enrollment visit, will be started on a conventional mood stabilizer just after randomization. These participants should be on a mood stabilizer for at least 7 days before starting study medication.

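### A 3BD sample up to about a month old can, by implication, serve as the FLAME biomarker baseline, so a tapered patient's baseline may predate the antidepressant washout

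*Combined protocol and SAP*

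**What the plan says.** The baseline column of Table 4 carries an asterisk. Its footnote, in the Biospecimen section, begins "See 1.b. in this section", and item 1.b is the one on epigenetic and metabolomic/proteomic biomarkers. The footnote then sets the condition for a new draw: the participant did not join the 3BD Disease Risk Program, "or did so more than a month before enrolling the FLAME Study; a separated blood draw of 55 mL". That draw "will be collected as baseline sample". Item 1.b describes the FLAME biomarker blood as matching what 3BD collects.

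The Screening visit section sets the timetable for anyone taking an antidepressant at screening. If stopping is acceptable, "then the antidepressant will be tapered off in 1 week". It continues: "The participant will have to be at least 7 days completely off the antidepressant before randomization", and "the total number of days from screening to enrollment for these participants will be 14 days".

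The sample feeds Aim 3: "To identify blood and brain metabolites associated with treatment response to lamotrigine (n=200) and fluoxetine (n=200) in bipolar depression". Hypothesis 3 extends this to epigenetic and metabolomic/proteomic markers. Table 5 shows that the 55 mL set yields serum, plasma, white-cell proteins, RNA and PBMCs as well as DNA.

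**The concern.** The reuse rule is set by calendar time since joining 3BD, not by the washout. A month is about twice the 14-day taper and washout interval, so a 3BD sample that meets the rule can come from a time when the patient was still taking the old antidepressant, or was part-way through the taper.

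Genotype does not change with time, so this is harmless for germline DNA. Metabolites, proteins, RNA and epigenetic marks can vary with drug exposure and clinical state when blood is taken. The Schematic Design section wants both biomarkers that predict response and biomarkers that are targets of response, so the baseline sample matters both as a predictor and as a pre-treatment reference. If some baselines are washed out and same-day while others are on-drug and weeks old, the pre-treatment measurement does not mean the same thing for every participant. Nothing in the plan requires a reused sample to postdate the washout, or requires drug exposure at sampling to be recorded.

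**Working it through.** **1. Volumes in Table 4.** Baseline 15 + 55 = 70 mL; week 2, 55 + 10 = 65 mL; week 4, 55 + 10 = 65 mL; week 16, 10 mL. The sum is 70 + 65 + 65 + 10 = 210 mL, which reproduces the stated total. It already contains a 55 mL baseline biomarker draw.

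**2. The footnote's 245 mL.** This is given as the total for a participant who needs the separate draw.
- Adding 55 mL to the Table 4 total gives 210 + 55 = 265, not 245.
- Laboratory tests, three biomarker draws and the week-16 drug level give 15 + 3 × 55 + 10 = 190. Then 190 + 55 = 245.

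So 245 mL leaves out the week-2 and week-4 drug-level tubes (2 × 10 = 20 mL) and counts a second 55 mL baseline draw.

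**3. Reuse window against washout.** Inputs: a month of 28 to 31 days (assumed), counted back from the enrollment visit; one week of taper; at least seven days off drug; 14 days in all (Screening visit section). The rule refers to the date of joining 3BD; that 3BD blood is drawn at about that date is an assumption.

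| Days before enrollment | State of a tapered patient | Number of days | Share of window |
|---|---|---|---|
| 1-7 | off drug (guaranteed) | 7 | 23-25% |
| 8-14 | in taper | 7 | 23-25% |
| 15 to 28-31 | before taper | 14-17 | 50-55% |

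Days before the guaranteed drug-free period: 28 - 7 = 21 to 31 - 7 = 24. Shares: 21/28 = 75% and 24/31 = 77%. Before the taper: 14/28 = 50% and 17/31 = 55%.

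**4. If enrolling means consent or screening.** Every reused sample then predates the taper and can be 28 + 14 = 42 to 31 + 14 = 45 days old at randomization.

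**5. Does other text close the gap?** The Screening visit section and item 1.b name only weeks 2 and 4 for the additional biomarker samples. After the taper, the plan reassesses eligibility with rating scales and names no repeat biomarker draw. The Data Analysis section sets out models for SNPs only; its concomitant-medication covariate does not clearly cover an antidepressant stopped before enrollment.

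**6. Residual drug after washout.** With the half-life of about 4 to 16 days quoted under Fluoxetine pharmacogenomics and simple exponential decay (metabolite ignored), the fraction left after seven days is 0.5^(7/4) = 0.30 to 0.5^(7/16) = 0.74. Even a sample taken after the washout need not be free of earlier fluoxetine.

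**The case against.** The strongest reply is that reuse is never stated outright and that other text points to a fresh draw for everyone. The Biospecimen section says 70 mL is taken at baseline, which is 15 + 55, with no exception for recent 3BD participants. Table 4 lists 55 mL at baseline and Table 1 marks a blood draw at enrollment. The 190 + 55 arithmetic treats the separate draw as additional to a baseline draw already counted. This ambiguity is real. But a fresh draw for everyone would leave the one-month condition without purpose, and the asterisk qualifies the very column that lists the 55 mL.

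The second reply is that the harm is narrow and partly hypothetical. No metabolomic analysis or change-from-baseline contrast is specified. Randomization should balance reuse between arms in expectation, so in an arm comparison it would act mainly as noise. This too stands, but Aim 3 concerns association with response, and randomization between arms does not make reused and fresh baselines comparable across responders and non-responders.

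Several stronger inferences are tempting and are not supported:
- **A count of affected participants.** The documents do not say how many join 3BD within a month of FLAME. The 49.8% in the Introduction concerns initial treatment with an antidepressant, not use at FLAME screening. Draw dates need not be spread evenly over the month.
- **That any sample taken before screening is an on-drug sample.** The antidepressant may have been started after the 3BD draw.
- **That the fluoxetine signal would be falsely small.** This presumes an analysis the plan does not describe.
- **That 245 mL cannot be derived from Table 4.** It can, as shown, though not consistently with the 210 mL total.

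**Conclusion.** The point holds as an implied gap. On the natural reading of the footnote, a 3BD sample from within about a month may stand as the biomarker baseline, and for a tapered patient 21 to 24 of the 28 to 31 permitted days fall before the guaranteed seven days off drug. This rests on three assumptions: reuse is what the footnote intends, 3BD blood is drawn at about 3BD enrollment, and the month is counted back from the enrollment visit. Counting from screening makes the overlap worse.

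The reach is limited to tapered patients who recently joined 3BD and take part in the optional biomarker studies; their number cannot be derived from the documents. The SNP analyses of Aims 1 and 2 are untouched. The change is still worth making, because a baseline sample missed before the first study dose cannot be recovered. If a fresh draw for everyone was intended, the footnote needs to say so.

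**What to change.** In the Table 4 footnote, limit reuse of a 3BD sample to germline DNA. For every participant in the biomarker studies, collect the 55 mL baseline already listed in Table 4 at the enrollment visit, after washout and before the first study dose. Record the prior antidepressant and its stop date at sampling, because some carry-over from earlier fluoxetine may remain and the analysis should be able to account for it. Reconcile the 210 and 245 mL totals, stating whether the week-2 and week-4 drug-level tubes are included and whether a second baseline draw is meant.

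The cost is a short protocol edit, one added data item, and 55 mL more blood with its processing for recent 3BD enrollees, at a visit where Table 1 already schedules a blood draw.

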## Statistical Considerations

### Endpoints:

There are two primary endpoints for the 3BD Clinical Program namely treatment response and adverse events. Detailed information on possible contributing factors (i.e. age, gender, previous treatment history, alcohol abuse or dependence comorbidity, seasonal and/or circadian rhythm, preceding stressful event, etc) will be evaluated.

### Data Analysis:

We will investigate association between the primary endpoints a set of SNPs in the gene candidates and/or GWA studies to evaluate a greater number of SNPs and bioinformatics tools to perform pathway analysis. Primary analyses will evaluate the association between treatment response and adverse events phenotypes and SNPs in candidate genes by comparing genotype frequencies between the treatment responder and non-responder groups and the presence/absence of adverse events, using logistic regression, assuming a log-additive model for

allele effects. Logistic regression will enable multivariate analyses, and in particular to assess genetic effects on treatment response and adverse events, while adjusting for other possible risk factors, and modeling gene-environment interactions. Covariates modeled in the analysis will include age of onset of bipolar disorder, and presence or absence of circadian rhythm liability, concomitant medication, alcohol abuse or dependence comorbidity (lifetime), stressful events (defined as presence or absence of any stressful event in the last 12 months and as a score that will summarize the number of stressful events in the prior 12 months), binge eating, body mass index measures and other relevant phenotypes.

A large majority of the Mayo Clinic Rochester participant population is white, non-Hispanic. However, due to the greater ethnic diversity of participants at the other sites, we anticipate that approximately 25% of our sample may come from other racial or ethnic groups. Therefore, all of our genetic analyses will be adjusted for self-reported ethnicity and secondary analyses will be undertaken within ethnically homogeneous subgroups.

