In terms of risk, antidepressant agents have been associated with the emergence of mania in participants with bipolar disorder; this infrequent recurrence can often be a devastating consequence of attempting to ameliorate depressive symptoms. It is generally thought that all antidepressants have this potential and, therefore, may worsen the acute and overall course of bipolar disorder. It is generally thought that newer antidepressants, as compared with tricyclic antidepressants (TCAs), have a lower propensity to induce mania in participants treated for bipolar depression. Pooled data from several clinical trials reported a manic switch in 9 of 242 (3.7%) participants with bipolar depression treated with selective serotonin reuptake inhibitors (SSRIs), 14 of 125 (11.2%) treated with TCAs ( $P<0.01$  vs. SSRIs), and 2 of 48 (4.2%) treated with placebo (Peet, 1994). Fluoxetine switch rate varied substantially between 0% (Cohn et al., 1989) and 50% (Amsterdam and Schults, 2005) in monotherapy studies for bipolar depression. It is clear from the limited and heterogeneous studies performed to date, that further investigation is needed to determine the efficacy and safety of fluoxetine in the treatment of bipolar depression.

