#### Possible Risks for study medications

Fluoxetine is FDA approved for unipolar depression in adult and pediatric populations. Double-blind, randomized controlled studies in monotherapy (Cohn et al., 1989) and as a combination with olanzapine (Tohen et al., 2003; Brown et al., 2006) have found it effective for the treatment of bipolar depression. All participants will be informed of all known side effects. The most commonly observed side effects of fluoxetine are lightheadedness, fainting, dizziness, confusion, hallucinations, rhinitis, dry mouth, tremor, nausea, ejaculation disorder (primarily ejaculatory delay), impotence, fatigue, diarrhea, sleep disorders (somnolence), and sweating. The FDA has issued a black box warning for fluoxetine regarding antidepressants increased the risk compared to placebo of suicidal thinking and behavior (suicidality) in children, adolescents, and young adults in short-term studies of major depressive disorder and other psychiatric disorders.

For bipolar depressed participants participating in the open lamotrigine trial, lamotrigine is FDA approved for the maintenance phase of bipolar disorder. Although we are using the FDA bipolar drug in a different phase than its original indication, there is placebo-controlled data showing efficacy in the phase that we are studying (Calabrese et al., 1999; Frye, M.A. et al., 2000).

Most side effects of lamotrigine are mild and go away without stopping the drug. The most frequent side effects include dizziness, muscular incoordination, drowsiness, headache, insomnia, double-vision, blurred vision, bradycardia (slow heart rate), nausea, vomiting. If any of these side effects are experienced, the subject must not drive a motor vehicle until these symptoms have stopped.

Approximately 16% of participants receiving lamotrigine for Bipolar Disorder in premarketing trials discontinued therapy because of an adverse experience – most commonly due to rash (5%) and mania/hypomania/mixed mood adverse events (2%).

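### If adverse events occur at the lower rates the protocol cites (about 7 to 14 per arm of 200), the planned logistic model with at least nine adjustment terms gives distorted tests, and no sparse-event method or power figure is stated.

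*Combined protocol and SAP*

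**What the plan says.** The Endpoints section states: "There are two primary endpoints for the 3BD Clinical Program namely treatment response and adverse events". Under Aims, the adverse-event phenotypes are "rash emergence and antidepressant induced mania (AIM+) to lamotrigine (n=200) or fluoxetine (n=200) respectively in bipolar depression", so each is studied within one arm of 200.

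The Data Analysis section gives one method for both endpoints: genotype frequencies are compared "using logistic regression, assuming a log-additive model for" allele effects. On adjustment it says: "Covariates modeled in the analysis will include age of onset of bipolar disorder, and presence or absence of circadian rhythm liability, concomitant medication". The list goes on to lifetime alcohol comorbidity and stressful events (both as yes/no and as a count), and ends with "binge eating, body mass index measures and other relevant phenotypes". Every genetic analysis is also adjusted for self-reported ethnicity, and gene-environment interactions are to be modelled. The section names no test (Wald, likelihood-ratio or other), no penalised or exact method, no limit on covariates and no rule for separation.

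The Power Statement covers response only: 150 responders against 150 non-responders, significance level 5×10⁻⁵ for 1000 SNPs, 80% power at odds ratio (OR) 2.90 and MAF 0.2. No event rate or detectable effect is given for adverse events.

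**The concern.** Maximum-likelihood logistic regression relies on large-sample theory that needs enough events for each fitted coefficient. The response endpoint has them. The adverse-event endpoint may not: at 10 events, nine adjustment terms plus the SNP leave one event per coefficient.

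Two things then go wrong. Some coefficients have no finite estimate, and the common tests no longer hold their nominal level, with Wald and likelihood-ratio erring in opposite directions. Because the plan names neither, the error rate for this primary endpoint depends on a choice left open until the data are in hand. A reader could also carry the 80% power claim over to Aim 2, where it does not apply.

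**Working it through.** **Event counts.** Expected events = 200 × rate.

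- Stopping for rash in premarketing trials, 5% (Possible Risks for study medications): 10.
- Pooled SSRI switch, "9 of 242 (3.7%) participants with bipolar depression treated with selective serotonin reuptake inhibitors" (Fluoxetine: efficacy and safety): 7.4.
- Hypomania in the open fluoxetine monotherapy study, 4.1% (same section): 8.2.
- SSRI switch in the meta-analysis, 7% (Fluoxetine pharmacogenomics): 14.
- Antidepressant-induced mania (AIM+) in community practice, up to 30% (Introduction): 60.

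**Adjustment terms.** Age of onset, circadian liability, concomitant medication, alcohol, stress yes/no, stress count, binge eating and body mass index make 8; ethnicity makes 9. This allows one term each for medication and ethnicity. Multi-level coding of those two gave 13 in one simulated variant.

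**The plan's own figure.** For a log-additive model with Hardy-Weinberg genotype frequencies p_g (g = 0, 1, 2) and overall outcome rate φ:

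- logit π_g = α + g·ln(OR), with α set so that Σ p_g π_g = φ
- NCP = 2N[H(φ) − Σ p_g H(π_g)], where H(x) = −x ln x − (1−x) ln(1−x)
- power = P(χ²₁(NCP) > 16.45), 16.45 being the two-sided 5×10⁻⁵ point; 80% power needs NCP = 23.98

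With N = 300, φ = 0.5, MAF 0.2 and OR 2.90: π = 0.399, 0.658, 0.848; NCP = 24.07; power = 80%. The stated figure reproduces. The second one (OR 2.35) reproduces at MAF 0.4; the printed MAF of 2.35 looks like a misprint.

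**Same formula for adverse events, N = 200, MAF 0.2, unadjusted.**

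| Events | NCP at OR 2.90 | Power | OR for 80% power |
|---|---|---|---|
| 7 | 3.24 | 1.2% | 24 |
| 10 | 4.48 | 2.6% | 13.7 |
| 14 | 6.00 | 5.4% | 9.2 |
| 60 | 15.66 | 46% | 3.8 |

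A simulated unadjusted trend test needs OR about 12 at 10 events and about 8 at 14, hence the range of roughly 8 to 14. At MAF 0.4 and 10 events the formula gives about 18, and other variants up to 21.

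**Test size in the adjusted model.** Simulation under no SNP effect, N = 200. Covariates are unrelated to the outcome, and their prevalences are assumptions. LRT is the likelihood-ratio test.

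| Events, terms, MAF | Any coefficient separates | SNP separates | Wald at 0.05 / 0.001 | LRT at 0.05 / 0.001 |
|---|---|---|---|---|
| 10, 9 terms, 0.2 | 35% | 2.7% | 0.036 / 0.0002 | 0.076 / 0.0028 |
| 10, 13 terms, 0.2 | 90% | 2.9% | 0.039 / 0.0002 | 0.087 / 0.0043 |
| 10, 9 terms, 0.05 | 56% | 37% | 0.038 / 0.0006 | 0.044 / 0.0012 |
| 20, 9 terms, 0.2 | 6% | 0.1% | 0.045 / 0.0007 | 0.061 / 0.0020 |
| 60, 9 terms, 0.2 | 0% | 0% | 0.052 / 0.00085 | 0.057 / 0.0018 |
| 10, 9 terms, 0.2, Firth | 0% | 0% | – | 0.045 / 0.00055 (profile likelihood) |

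Replicates: about 9,000 for the 13-term row, 11,000 for Firth, 20,000 to 21,000 otherwise. Another nine-covariate simulation gave 23% separation, LRT size 0.33% at nominal 0.1%, and Firth 0.11%.

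**Power in the adjusted model**, OR 2.90, MAF 0.2, 5×10⁻⁵ (Wald / LRT): 7 events 0.1% / 2.9%; 10 events 0.4% / 4.6%; 14 events 2.0% / 7.3%; 20 events 7.8% / 13.6%; 60 events 40% / 47%. Firth at 10 events gives 2.2% to 3.7%.

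**The case against.** The strongest objection is that 7 to 14 events is one end of the protocol's own range. The Introduction puts AIM+ at up to 30% in the community and argues that trial rates do not carry over. The fluoxetine section cites switch rates from 0% to 50%. The Power Statement claims a real-practice setting. The 5% figure counts stopping for rash, whereas Aim 2 concerns any rash emergence, so it may understate the endpoint. This stands, and makes the point conditional. In the other direction, hypomania is excluded at entry and bipolar I participants on fluoxetine must stay on a mood stabiliser. The 30% figure says nothing about lamotrigine rash.

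Three stronger readings are tempting, and the material does not support them.

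- A reader might infer that the model simply fails. Separation is mostly in nuisance covariates, which does not by itself invalidate the SNP test. The SNP separates in under 3% of fits at MAF 0.2, though in 37% at MAF 0.05.
- A reader might infer a specific inflation at 5×10⁻⁵. Nine-covariate runs gave 5 of 6,985, 3 of 20,991 and 8 of 40,984 null fits below that level, or about 14, 3 and 4 times nominal. These are too few rejections to quote a multiple.
- A reader might infer that Wald tests can never reach the threshold. Their power is small, not zero, and reaches 7.8% at 20 events.

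The plan is also partly silent. It says logistic regression without saying unpenalised. Entering all covariates together is the natural reading, not an explicit instruction. The 5×10⁻⁵ level appears only beside the response calculation. Finally, cutting covariates alone does much of the work: with one covariate, 9 of 12,994 null likelihood-ratio tests (0.07%) fell below 0.001.

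**Conclusion.** The concern holds conditionally. If events arrive at the lower cited rates, the planned analysis of one primary endpoint has roughly one event per coefficient. At about 10 events and MAF 0.2 the likelihood-ratio test is liberal (about 0.08 at nominal 0.05, about 0.3% at 0.1%) and the Wald test conservative. At 20 events the distortion is smaller. At 60 it is largely gone, with slight liberality of the likelihood-ratio test at nominal 0.1%.

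Separately from validity, power at the effect size used for response is a few per cent at 7 to 14 events and 40% to 47% at 60, and the plan does not say so.

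These results assume nine adjustment terms entered together, unpenalised fitting, assumed covariate prevalences, and 5×10⁻⁵ carried over to adverse events. The exact separation percentage moves with coding. The direction of the size errors at MAF 0.2 was the same in both nine-term and 13-term coding; at MAF 0.05 the likelihood-ratio test was close to nominal. This should be corrected before analysis.

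**What to change.** In the Data Analysis section, for the adverse-event endpoint:

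1. Specify Firth penalised logistic regression and name its profile-likelihood test as the test of the SNP.
2. Limit adjustment to self-reported ethnicity plus one or two covariates named in advance.

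In the Power Statement:

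3. Say that the 80% figure applies to response only.
4. State the assumed event rates for rash and AIM+, and give the detectable odds ratio as a range by event count and MAF. For example: roughly 8 to 14 at MAF 0.2 for 10 to 14 events, and 40% to 47% power at OR 2.90 with 60 events.

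The cost is a few lines of text and standard software, with no change to trial conduct. The downsides are a less favourable stated detectable effect for Aim 2 and less covariate adjustment. Firth addresses the error rate and separation only; the number of events still limits power.
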